TP-013, Rev 03 STAT PLAN SYNOPSIS FOR CLINICALTRIALS.GOV**HHC-IRB NUMBER: HHC-2020-0086****IRB APPROVAL DATE: 10/13/2020**

TITLE	Dislodgment Infiltration Phlebitis Prevention Eliminating Restarts (DIPPER)
SPONSOR	Lineus Medical
FUNDING ORGANIZATION	Lineus Medical
STUDY START DATE	June 2020
RATIONALE	Accidental IV catheter dislodgement and other mechanical complications (e.g., infiltration, phlebitis, infection, and occlusion) in hospitalized patients are very common. IV catheter mechanical complications increase costs and put patients at increased risk. SafeBreak Vascular is designed to separate into two pieces when a certain threshold of force is applied to an IV administration line. The purpose of this medical device investigation is to determine SafeBreak Vascular's impact on clinical care (e.g., delay of therapy) and its' impact on other IV catheter mechanical complications when compared to a control group of patients not using the device.
STUDY DESIGN	Prospective randomized clinical trial
PRIMARY OBJECTIVE	The primary objective of this study is to determine if the use of SafeBreak Vascular results in a delay in therapy that is non-inferior to the delay in therapy for the control group, and if so, if SafeBreak Vascular is superior.
SECONDARY OBJECTIVES	The secondary objective is to estimate the reduction of other peripheral IV (PIV) catheter mechanical complications including dislodgement, infection, phlebitis, infiltration, occlusion, as well as blood/fluid spillage and PIV restarts when compared to the control group.
NUMBER OF SUBJECTS	Up to 146 total (73 in each arm). This sample size allows for 10% of the subjects to abandon therapy before the normal completion of treatment.

SUBJECT DEVICE / INTENDED USE	SafeBreak is intended to stop fluid flow and prevent blood loss or fluid spillage in the event of excessive tension (4 ± 1 lbs of force) occurs across a peripheral IV administration line in adults and adolescent populations eighteen (18) years of age or older. SafeBreak Vascular may be used only with electronic pumps for intermittent infusion or continuous infusion.
CONTROL GROUP	Participants with current standard of care for peripheral IVs.
EFFICACY EVALUATIONS	The primary and secondary objectives address the efficacy of the SafeBreak device.
PRIMARY ENDPOINTS	The primary endpoint is the time to re-start therapy following a mechanical complication with the catheter.

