SECONDARY ENDPOINTS	Comparison of occurrence of mechanical complications (e.g., dislodgement, infection, infiltration, phlebitis, occlusion) as well as blood loss, fluid spillage and PIV restarts
SAFETY EVALUATIONS	The research team will evaluate all enrolled subjects at least twice daily for all adverse events and safety concerns and will document and communicate any concerns to the Investigator.
STATISTICAL ANALYSIS	
Primary Objective Test:
 
To demonstrate that the average time per 24 hours that therapy is delayed due to PIV mechanical complications is non-inferior with SafeBreak Vascular to that of the standard of care.
 
The secondary objective does not include a hypothesis test; estimation techniques will be used.

	
To test the Primary Objective:
 
 a. Of non-inferiority, the 24-hour delay of therapy due to PIV mechanical complications, SafeBreak Separations, and SafeBreak device failures of the SafeBreak group and PIV mechanical complications in the Control group will be compared with a non-inferiority Wilcoxon Rank-Sum test; b. Of inequality, the mean delay of therapy due to PIV mechanical complications, SafeBreak Separations, and SafeBreak device failures of the SafeBreak group and PIV mechanical complications in the Control group will be compared with a standard (inequality) Wilcoxon Rank-Sum test. 
To analyze Secondary Objective:
 
 a. The proportion of patients who experience PIV mechanical complications during the course of therapy will be estimated using a Kaplan-Meier time-to-event analysis. The proportions and counts of total mechanical complications will be compared between groups using a Chi-square analysis, Fisher's Exact Test, or Poisson regression as appropriate. b. Secondary endpoints include rates of IV restarts, blood/fluid spillage, dislodgement, infiltration, phlebitis, occlusion, and infection. The analysis population will be the Per Protocol population; the analysis method permits censoring at the time the patient exits or completes the study if this is prior to 7 days. 
Missing data that is not endpoint data will be ignored in reporting.

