RATIONALE FOR NUMBER OF SUBJECTS	
Sample size rationale:
 
A total of 66 patients per group will provide 80% power at $\alpha=0.05$ to demonstrate non-inferiority of SafeBreak. An additional 10% will be enrolled to accommodate drop-out prior to therapy completion, for a total of 146 subjects.

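### Secondary complication comparisons rest on a Per Protocol set that the posted synopses do not define; no all-randomised set is named, and the primary tests state no set

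*SAP*

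**What the plan says.** The trial is randomised, with up to 73 patients per arm. The SAP synopsis (Statistical Analysis, secondary objective, item b) names one analysis set, once: "The analysis population will be the Per Protocol population; the analysis method permits censoring at the time the patient exits or completes the study". The sentence goes on to limit this censoring to patients who leave or finish before day 7. Neither synopsis gives a membership rule based on deviations, device use, minimum exposure or early exit. No intention-to-treat, all-randomised or full-analysis set appears. The phrase about all enrolled subjects occurs only under Safety Evaluations, where it describes monitoring.

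The primary tests refer to the SafeBreak and Control groups without stating a set. The second of them, the superiority step, "will be compared with a standard (inequality) Wilcoxon Rank-Sum test".

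On the status of the secondary objective, the SAP says "The secondary objective does not include a hypothesis test; estimation techniques will be used". Item (a) nevertheless adds that "The proportions and counts of total mechanical complications will be compared between groups using a Chi-square analysis", Fisher's exact test or Poisson regression as appropriate.

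On early exit, Rationale for Number of Subjects says "An additional 10% will be enrolled to accommodate drop-out prior to therapy completion".

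**The concern.** Randomisation makes the arms comparable as assigned. A set chosen afterwards keeps that comparability only if the reasons for exclusion are unrelated to outcome, or act alike in both arms. Separations and device failures can occur only in the SafeBreak arm, so reasons for leaving a Per Protocol set could plausibly differ by arm. That is an inference from the design, not something the documents record.

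The secondary objective is to estimate a reduction in complications, so the estimate is the main product and a shift in it matters directly. The comparisons in item (a) would carry the same shift if made on the same set. Without a membership rule, a reader of the posted plan cannot tell whether exclusions may depend on events or on arm. Nor is it clear whether a patient who abandons therapy is removed, as the sample-size allowance might suggest, or kept and censored, as item (b) permits.

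**Working it through.** **The plan's own figure.** 66 × 1.10 = 72.6, rounded up to 73 per arm; 2 × 73 = 146. This matches. The base of 66 cannot be checked, because the synopses give no margin, standard deviation, assumed difference or sidedness.

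**Inputs for the illustration.** From the documents: 73 per arm, and 73 − 66 = 7 as a convenient number of exclusions. That 7 is a drop-out allowance; the plan ties it neither to events nor to one arm. Assumed: no true difference, and an event share p of 30, 40 or 50% in both arms. Crude proportions are used for simplicity, although item (a) also specifies Kaplan-Meier.

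**Case 1: 7 excluded from SafeBreak only, with twice the retained patients' risk r.** Then 73p = 66r + 7(2r) = 80r, so r = 73p/80 = 0.9125p. The risk ratio is about 0.91 at every p. The risk difference is −0.0875p, or −2.6/−3.5/−4.4 points.

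**Case 2: all excluded patients had events.** With s excluded from SafeBreak and c from control,

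RR = [(73p − s)/(73 − s)] / [(73p − c)/(73 − c)].

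Example at p = 0.30, s = 7, c = 0: (21.9 − 7)/66 = 0.226, and 0.226/0.300 = 0.75.

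| Excluded (SafeBreak, control) | RR at p = 30/40/50% | Risk difference, points |
|---|---|---|
| (7, 0) | 0.75 / 0.84 / 0.89 | −7.4 / −6.4 / −5.3 |
| (5, 2) | 0.89 / 0.93 / 0.95 | −3.2 / −2.7 / −2.3 |
| (4, 3) | 0.96 / 0.98 / 0.98 | −1.1 / −0.9 / −0.8 |
| (0, 7) | 1.33 / 1.19 / 1.12 | +7.4 / +6.4 / +5.3 |
| (7, 7) | 1.00 / 1.00 / 1.00 | 0 / 0 / 0 |

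In the (7, 7) row both arms read 22.6/33.6/44.7%, so the comparison is intact but the level is understated.

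**Case 3: exclusion unrelated to outcome.** The expected proportion stays at p in each arm, so there is no bias.

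**Scale against sampling error.** The 95% half-width for the risk difference at 73 per arm is 1.96 × √[2p(1 − p)/73] = 14.9/15.9/16.2 points. Every shift above is smaller, and the largest is about half of it.

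**Power if non-inferiority must pass in two sets.** Take the stated 80% at 66 per arm as correct and let all 73 give full data. By the normal approximation, the standardised effect grows by √(73/66) = 1.052:

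- One-sided 0.05: (1.645 + 0.842) × 1.052 − 1.645 = 0.970, power 83.4%.
- One-sided 0.025: (1.960 + 0.842) × 1.052 − 1.960 = 0.986, power 83.8%.

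For nested sets the correlation is √(66/73) = 0.951, and the bivariate normal probability of passing in both is 78.1% and 78.3% respectively.

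**The case against.** The strongest reply is that these are registry synopses. They use Per Protocol as a settled term, and a full plan may define it. That stands as a limit: the point concerns what is posted. It does not remove the choice itself, because the posted rule names Per Protocol and no all-randomised set.

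Second, a reader might infer that patients with complications or failed devices will be dropped. The documents do not support this. No text makes an event a reason for exclusion, the primary tests count separations and device failures as delay, and the population sentence itself permits censoring, so early leavers may well stay in. The (7, 0) case with events in every excluded patient is an extreme, not a forecast.

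Third, a reader might infer that the superiority claim, "and if so, if SafeBreak Vascular is superior", is already compromised. The Per Protocol sentence sits under the secondary objective, and the group names in the primary tests may simply mean the randomised groups. An effect on the primary tests would require that sentence to govern them too, which the text does not say. What stands is that their set is unstated.

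Fourth, Per Protocol is a recognised companion set for non-inferiority, so its use is not in itself an error. Also, an all-randomised set is not wholly free of difficulty. The protocol admits patients who only have plans for access or infusion; one who never starts has no therapy time, so delay per 24 hours is undefined. Chi-square and Fisher's tests do not use partial follow-up. Both observations are fair and shape the fix.

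**Conclusion.** The concern holds as a weakness of the stated analysis set: the secondary between-arm comparisons rest on an undefined post-randomisation set, with no all-randomised analysis beside it and no set stated for the primary tests. Bias is possible, but neither its presence nor its direction or size is established. Under the assumptions shown, seven one-sided exclusions move a true ratio of 1.00 to about 0.91 if the excluded patients carry double risk, and to 0.75–0.89 at the extreme; near-even event-related exclusion moves it to 0.96–0.98, and outcome-unrelated exclusion not at all. These shifts lie within sampling error, but a confidence interval does not account for a systematic shift. It should be fixed, with medium confidence; it is not evidence that the primary conclusion is unsafe.

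**What to change.** Replace the Per Protocol sentence so that:

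- All randomised patients, by assigned arm and with all observed follow-up (censored at exit, as the plan already permits), are the main set for the secondary comparisons and the superiority test.
- A stated rule covers randomised patients who never start an infusion and so have no therapy time.
- Per Protocol is kept as a companion set, defined before analysis, without using complications, separations or device failures as exclusion reasons. Exclusions are reported by arm and reason.
- Non-inferiority is reported in both sets. Whether both must pass is the sponsor's choice: it gives about 78% power against 80% for Per Protocol alone, if the stated 80% is right and all 73 per arm give full data.

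If a full plan already defines the set, add that definition to the posted synopsis. The cost is SAP wording and a second run of the same code, with no extra patients. The drawback is that time off the device may dilute a true difference in the all-randomised set.

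### Does the unstated non-inferiority margin undermine the claim of 80% power with 66 patients per arm?

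*SAP*

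**What the plan says.** Under Primary Objective, both documents ask whether delay with the device is "non-inferior to the delay in therapy for the control group, and if so, if SafeBreak Vascular is superior". Non-inferiority is thus the first step and superiority a conditional second step.

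Under Statistical Analysis, the SAP sets out to show that the "average time per 24 hours" of delayed therapy "is non-inferior with SafeBreak Vascular to that of the standard of care". For test (a), the two arms "will be compared with a non-inferiority Wilcoxon Rank-Sum test". Test (b) names "the mean delay of therapy due to PIV mechanical complications" and related device events as its target, and uses a standard rank-sum test. Of the secondary objective the SAP says: "The secondary objective does not include a hypothesis test; estimation techniques will be used". The same section then lists chi-square, Fisher and Poisson comparisons for it.

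The Rationale for Number of Subjects states: "A total of 66 patients per group will provide 80% power at" an alpha of 0.05, and adds a 10% allowance for drop-out, for a total of 146. Only non-inferiority is sized. The SAP file is headed "STAT PLAN SYNOPSIS FOR CLINICALTRIALS.GOV", and the Protocol file is likewise a registry synopsis of TP-013, Rev 03.

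**The concern.** A non-inferiority test is defined by its margin. Without one, a reader cannot say how much extra delay a positive result would exclude, and cannot check the sample size. If the margin were chosen after outcomes had been seen by arm, nothing in these two documents would expose it.

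A second difficulty sits behind the first. The stated target is an average or mean delay, but rank-sum tests do not compare means. If event-free patients score zero, much of the data may be tied, and the result then depends on how the margin enters the test. Subtracting it from every SafeBreak value would push that arm's zeros below the control arm's zeros. Event-free SafeBreak patients would then outrank event-free controls merely because of the subtraction.

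**Working it through.** **1. Drop-out step.** Inputs from the SAP: 66 per arm and 10%. 66 × 1.10 = 72.6, rounded up to 73, and 2 × 73 = 146. The plan's total is reproduced. Dividing instead gives 66 / 0.9 = 73.3, so 74 per arm and 148 in total. With 73 enrolled and 10% lost, 73 × 0.9 = 65.7 remain, so the two conventions differ trivially.

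**2. Can 66 be reached?** A forward calculation is impossible without a margin and an SD, so work back from 66. With no true difference and margin m in SD units:

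n per arm = 2(z_alpha + z_power)² / m², divided by 3/π = 0.955 for the rank-sum test under normality.

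- One-sided 0.025, m = 0.5: 2 × (1.960 + 0.842)² / 0.25 = 62.8, and 62.8 / 0.955 = 65.8, so **66**.
- One-sided 0.05, no efficiency factor: m = (1.645 + 0.842) × √(2/66) = **0.433**.
- One-sided 0.025, no factor: m = (1.960 + 0.842) × √(2/66) = 0.488.

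The SAP does not say which of these, if any, was used. Without the factor, a margin of 0.4 SD would need 78 per arm (one-sided 0.05) or 99 (0.025). A margin of 0.6 SD would need 35 or 44. So 66 is neither confirmed nor refuted.

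**3. Would another test be better?** Everything in this step rests on assumptions found in neither document: event-free patients score zero, non-zero delays are lognormal, and event share and coefficient of variation (CV) are as listed. Settings: 66 per arm, 10,000 runs, one-sided 0.025, margin 0.488 SD. Each cell gives the false-pass rate, with the SafeBreak mean worse by the whole margin through longer delays, then the power with identical arms (both in %).

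| Event share, CV | Rank-sum, margin subtracted | Rank-sum, floored at zero | Rank-sum, ratio margin | Welch interval for means |
|---|---|---|---|---|
| 30%, 0.5 | 99.4 / 100 | 0.9 / 5.5 | 2.5 / 10.1 | 4.1 / 79.9 |
| 30%, 1 | 99.7 / 100 | 1.7 / 15.2 | 2.5 / 7.7 | 6.1 / 80.6 |
| 50%, 0.5 | 50.1 / 94.5 | 0.7 / 18.6 | 2.5 / 28.0 | 3.0 / 79.6 |
| 50%, 1 | 78.8 / 99.9 | 2.8 / 46.9 | 2.3 / 18.1 | 4.5 / 81.2 |
| 70%, 0.5 | 8.0 / 82.9 | 0.9 / 51.2 | 2.2 / 52.6 | 2.7 / 79.0 |
| 70%, 1 | 39.3 / 99.3 | 7.7 / 82.7 | 2.5 / 37.3 | 4.1 / 80.0 |

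The subtracted form is unsafe in this model, although it passes in only 1.3 to 33.5% of runs (event share 30 to 50%) when the worsening comes through more events. Skew contributes as well: with no zeros at all it still passes in 6.7% (CV 0.5) to 34.4% (CV 1).

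The Welch interval keeps its power but not its level. Its false-pass rate rises to about 5 to 8% at a 20% event share and about 8 to 12% at 10%. There the ratio form stays at 2.4 to 2.7%, with only 3 to 6% power. No form is best throughout.

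**4. Superiority step.** Test (b) uses no margin, so none of this affects it. With identical arms, an unshifted rank-sum test at one-sided 0.05 rejected in 5.2%, 5.2% and 6.0% of 2,000 runs with 0%, 50% and 70% zeros.

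**The case for a change.** The strongest case for a change is that the sponsor published the sample size, power and alpha but left out the quantity that gives them meaning. No redaction mark explains the omission. Writing it down would cost a few lines and one power calculation. With sample size and margin both fixed, the table shows power running from 5.5% to 100% according to the form of the test, so giving a margin alone would not settle the matter.

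Much of this stands. The inputs are absent, the power cannot be checked here, and the subtracted form would be a poor choice if zeros are common.

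What does not stand is the step from there to a defect in the plan. The SAP nowhere says the margin is subtracted from every value. Nor does it say that event-free patients score zero. Under Primary Endpoints, the outcome is the time taken to resume therapy after a catheter complication, which could be read as leaving those patients out. The per-24-hour wording under Statistical Analysis points the other way. The large false-pass rates therefore belong to one unstated form in assumed data. The remedy that would alter the method exchanges one weakness for another.

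**Conclusion.** No change to the plan follows. The gap is genuine, but it is missing detail in a document that calls itself a synopsis. The stated 66 is attainable under ordinary inputs: 0.5 SD at one-sided 0.025 with the 3/π factor, or about 0.43 SD at one-sided 0.05 without it. Setting down the margin, sidedness and variability would record what the calculation must already have used. An analyst carrying out test (a) has to fix the margin form and the treatment of ties in any case, and can see that subtracting a margin from zero delays gives impossible negative values. Moving to an interval for the mean difference is a fair trade-off rather than a correction: it matches the stated target and keeps about 80% power, but is liberal with skewed data and few events.

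This rests on two assumptions: that the full TP-013, which is not available here, holds the margin and was settled before outcomes were compared by arm, and that the simulated event shares and CVs illustrate sensitivity rather than describe this trial. If the full protocol held no margin either, the conclusion would be different.
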